6.4.5.2. Maximum Duration

Maximum duration is the longest duration within a reporting group (eg, SOC).

6.4.5.3. Mean Duration

Mean duration is the average duration within a reporting group (eg, SOC), derived as the total duration divided by the number of events in the reporting group.

6.4.6. Change-from-baseline

Change-from-baseline is calculated as (post-baseline result – baseline result).

Percent change-from-baseline is calculated as (100 * change-from-baseline/baseline result).

If either the baseline or the post-baseline result is missing, the change-from-baseline and percentage change-from-baseline are also missing.

6.4.7. ALIS Treatment

Study drug (ALIS) was the only study treatment provided by the sponsor. Therefore, compliance can only be determined for ALIS and then compliance can only be determined based on vial counts.

The MDR treatments are captured in the concomitant medication log, but compliance with dosing was not tracked during the study. However, since subjects came to the study on MDR and continued MDR treatment through the study and after leaving the study, duration of MDR is not informative.

6.4.7.1. Duration of ALIS

Duration of ALIS will be derived as the last dose – first dose + 1 as captured on the CRF.

6.4.7.2. Compliance with ALIS

Because ALIS is a once a day dosing, prescribed number of doses is the same as the duration. Therefore, compliance with ALIS will be derived as the number of vials taken / duration of ALIS. Protocol allowed ALIS treatment interruptions, were not captured in a manner that these interruptions can be accounted for in compliance.

6.4.8. CTC Grading of Audiology Results

Hearing loss will be graded based on the CTC grading criteria in [Table 3](#) .

Table 3: Hearing Loss CTC Grade

Grade	Criteria
1	Threshold shift of 15 - 25 dB averaged at 2 contiguous test frequencies in at least one ear.
2	Threshold shift of >25 dB averaged at 2 contiguous test frequencies in at least one ear.
3	Threshold shift of >25 dB averaged at 3 contiguous test frequencies in at least one ear; therapeutic intervention indicated.
4	Decrease in hearing to profound bilateral loss (absolute threshold >80 dB hearing loss at 2 kHz and above); non-serviceable hearing.

The baseline hearing test is the threshold for deriving the grade. Subjects who do not meet any of the above CTC grades will have a CTC grade of zero (0).

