#### **7.1.6 Audiology**

##### **7.1.6.1 Methodology**

Frequencies of 250, 500, 1000, 2000, 4000, and 8000 Hz will be evaluated for each ear using air conduction. If audiometry findings are an AE Grade 2 or higher (per the Common Terminology Criteria for Adverse Events [CTCAE] Version 4.0 guideline), an additional audiometric evaluation should be conducted at the next scheduled visit.

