6.3. Baseline Definition

Any non-missing value from any procedure at a subjects EOT visit in study INS-212 will be denoted as their baseline value. If that result from the aforementioned visit is missing, then the non-missing value at the subsequent visit in the INS-312 study.

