9.7. Audiology Tests

All audiology testing data summaries and tabulations will be based on the safety population.

At each visit, only those subjects providing data at the visit will appear on the tables.

The actual, baseline and change-from-baseline audiology test results at each will be summarized (n, mean, standard deviation, median, minimum, and maximum) by visit, frequency, and ear for each prior treatment and overall. At each visit the baseline summary will reflect those subjects who provided data at that visit.

The audiology results will be tabulated (number and percentage of subjects) by CTC grade (0, 1, 2, 3, 4) and total for either, left, and right ears within treatment and total groups.

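### Hearing-loss grade 0 is a residual class with no evaluability condition, so a tested subject or ear whose shift from a pre-dose Baseline cannot be computed can be tabulated as having no hearing loss

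*SAP*

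**What the plan says.** Protocol 7.1.6.1 sets the test: "Frequencies of 250, 500, 1000, 2000, 4000, and 8000 Hz will be evaluated for each ear using air conduction". The schedule of events places it on Day 1, at Month 6 and at Month 12/EOT, and a footnote requires the Baseline test before dosing on Day 1.

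Final SAP 6.4.8 (Table 3) defines grades 1 to 3 as a threshold shift averaged over two or three contiguous frequencies in at least one ear. The reference is fixed: "The baseline hearing test is the threshold for deriving the grade". Grade 4 differs in being bilateral and absolute ("absolute threshold >80 dB hearing loss at 2 kHz and above"), so it needs no Baseline. Everyone else falls into one class: "Subjects who do not meet any of the above CTC grades will have a CTC grade of zero (0").

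Three other sections bear on this:

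- Section 6.4.6: "If either the baseline or the post-baseline result is missing, the change-from-baseline and percentage change-from-baseline are also missing". It does not say what grade follows from a missing shift.
- Section 6.3, for a missing INS-212 EOT value: "If that result from the aforementioned visit is missing, then the non-missing value at the subsequent visit in the INS-312 study". Nothing limits that value to one taken before dosing.
- Section 9.7: "At each visit, only those subjects providing data at the visit will appear on the tables", and "The audiology results will be tabulated (number and percentage of subjects) by CTC grade (0, 1, 2, 3, 4) and total". The tabulation is made for either, left and right ears. No row is provided for a grade that could not be determined.

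**The concern.** A subject who has an audiogram at the visit but no usable Baseline passes the section 9.7 filter, meets none of the shift criteria, and lands in the residual class. The same can happen when thresholds are missing at some frequencies and the pairs that remain show no qualifying shift. In both cases an undetermined result is printed as absence of toxicity.

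This runs against the SAP's practice elsewhere. Missing cultures before conversion count as positive (6.5.1.1), and incompletely dated adverse events default to treatment-emergent (6.5.3). Here the default favours the drug.

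Ototoxicity is an adverse event of special interest (Protocol 8.3), and audiology is a named safety variable in the protocol synopsis. Hearing loss has its own tabulation and shift table (SAP Tables 14.3.11.2 and 14.3.11.3).

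**Working it through.** The plan states no figure to reproduce. The check is to apply Table 3 to constructed audiograms and then work out what added zeros do to a percentage.

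**Inputs.** Six frequencies per ear (Protocol 7.1.6.1) give 5 contiguous pairs and 4 contiguous triples. Grades 1 to 3 are taken on their numerical part only. All audiograms below are hypothetical. Baseline in both ears, from 250 to 8000 Hz, is 20, 20, 20, 25, 30, 40 dB.

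**Reference case, full data.** The left ear at the visit is 20, 20, 25, 40, 65, 80, so the shifts are 0, 0, 5, 15, 35, 40. The 2/4/8 kHz triple averages (15 + 35 + 40)/3 = 30 dB, which exceeds 25: grade 3.

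**Variants.** The literal rule gives 0 whenever no grade is met. The evaluable rule gives 0 only if every contiguous pair can be computed, and otherwise NE (not evaluable).

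| Case | Literal | Evaluable rule |
|---|---|---|
| Reference case, full data | 3 | 3 |
| Same visit, no Baseline | 0 | NE |
| Same visit, used as its own Baseline under 6.3 (all shifts 0) | 0 | 0 |
| 4 kHz missing in both ears, 8 kHz shift 80 − 40 = 40, other shifts 0 | 0 | NE |
| No Baseline; 85 dB at 2 kHz, 4 and 8 kHz missing, both ears | 0 | NE |
| No Baseline; 85, 90, 95 dB at 2, 4, 8 kHz, both ears | 4 | 4 |
| 8 kHz missing; left 2 and 4 kHz shifts 5 and 35, pair mean 20 | 1 | 1 |
| 4 and 8 kHz missing in one ear; 1 and 2 kHz shifts 20 and 35, pair mean 27.5 | 2 | 2 |
| 4 kHz recorded as >70 and used as 70; triple mean (0 + 40 + 40)/3 = 26.7 | 3 | 3 |

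The third row shows that an evaluability condition alone is not enough. If no Day 1 test exists, the next scheduled audiogram is Month 6. Used as Baseline, it hides any shift at Month 6 and leaves loss before Month 6 out of the Month 12 shift. Only a pre-dose limit on Baseline removes this.

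The last four rows show the limits of the problem. Missing frequencies lead to 0 only if the values are stored as missing and every remaining pair falls short.

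**Direction.** Take the denominator as subjects tested at the visit, as 9.7 implies. Let x be the number graded 1 to 4 among N tested, of whom u are not evaluable and printed as 0. The table shows x/N. Excluding the u gives x/(N − u), which is at least x/N. Grading them correctly, with k truly affected, gives (x + k)/N, also at least x/N.

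**Size, on assumed inputs.** If the true rate is p and a share m is not evaluable for reasons unrelated to hearing, the table shows p(1 − m). Neither input is in the documents.

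| True rate p | m = 2% | m = 5% | m = 10% | m = 20% |
|---|---|---|---|---|
| 5% | 4.9% | 4.75% | 4.5% | 4.0% |
| 10% | 9.8% | 9.5% | 9.0% | 8.0% |
| 20% | 19.6% | 19.0% | 18.0% | 16.0% |

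**The case against.** The strongest reply is that the route to a false grade 0 is narrow. A pre-dose Baseline audiogram is mandatory, and section 6.3 supplies a substitute when the INS-212 value is missing. Losing 8000 Hz in one ear removes only 1 of 5 pairs and 1 of 4 triples there, and leaves the other ear intact. Grade 4 needs no Baseline. Because 6.4.6 makes the shift missing, a programmer could reasonably leave the grade missing too. Harm would also show elsewhere: decibel summaries by visit, frequency and ear (9.7), the audiology listing (16.2.13), mandatory reporting of hearing loss of CTCAE Grade 2 or higher as an adverse event (Protocol 7.1.6.2), and the ototoxicity terms in SAP Table 6.

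Most of this stands, and it limits the size. It does not remove the defect. Section 6.3 has no pre-dose condition, so its substitute can itself produce the zero. Leaving the grade missing departs from what 6.4.8 says and has no row in the table.

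A reader might go further and infer that the worst hearing losses are the ones hidden, because severe loss makes a threshold unmeasurable. The documents do not support that. They do not say how no response is stored. Section 6.1 uses the numeric part of values recorded with < or >, although it is worded for summaries of continuous variables. The constructed severe case that fell to 0 needed both a missing Baseline and missing values at 4 and 8 kHz. With the Baseline above, its 1/2 kHz pair averages (0 + 60)/2 = 30 dB, which is grade 2. Likewise, with 14 affected among 140 tested (assumed), a fall from 10.0% to 8/140 = 5.7% requires 6 of the 14 to meet no grade at any usable pair in either ear. Nothing in the documents supports that share.

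**Conclusion.** The point holds as a defect in a stated rule. Read literally, 6.4.8 and 9.7 together allow an undetermined hearing grade to be reported as grade 0, and 6.3 can produce the same result through a post-dose Baseline. It would be too strong to say that every subject with a missing threshold is reported as having no hearing loss, or that misclassification is certain.

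Counting undetermined grades as 0 can only lower the tabulated rate. The amount cannot be derived from the documents, and the rates in the working rest on assumed inputs. It is probably small, because Baseline audiology is mandatory and hearing adverse events are reported separately. The change is worth making because the bias runs one way, it concerns an event of special interest, and correcting it is cheap.

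**What to change.** In final SAP 6.4.8:

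- Assign grade 0 only when pre-dose Baseline and visit thresholds allow the contiguous-frequency shifts to be evaluated and no grade is met.
- If a grade 1 to 4 criterion is met on the available frequencies, assign that grade.
- Otherwise assign *not evaluable*. Apply the same rule to each ear in the left and right tabulations.
- Before grading, code any no response as the audiometer's maximum output at that frequency.

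In 6.3, limit the audiology Baseline to values taken before the first INS-312 dose. Section 13.6 of the SAP for the accelerated submission already defines it that way.

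In 9.7, show *not evaluable* as its own row, exclude it from the percentage denominator, and name that denominator, since the default in section 9 is the Safety Population.

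The cost is a few sentences and one derivation change on data already collected, plus confirming the maximum outputs if they were not recorded. The denominator becomes slightly smaller and the rate possibly less favourable. Keeping positives with incomplete data while setting aside incomplete negatives leans slightly upward, but the new row lets a reader bound the rate between x/N and (x + u)/N.

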6.4.9. Visit Windows

Nominal visit windows will be used for all visits, except for EOT and EOS visits. Because EOT and EOS visits are conducted in place of the planned visit for subjects who prematurely end treatment or study participation, these visits also need to be mapped to the coincident visit.

For example, a subject discontinues treatment at the Month 4 visit. The site will conduct the EOT visit at Month 4 rather than the Month 4 visit, but for analysis purposes this visit should be used for the Month 4 summary as well as the EOT summary. Similarly, for the EOS visit. Thus, should it be appropriate, the EOT and EOS visit need to be mapped to the corresponding visit. Should the EOT or EOS visit map to a time that doesn't coincide with a scheduled visit, it will not be mapped.

Subjects who prematurely discontinue from the study, may not have an EOT visit. In this case the EOS visit will also be the EOT visit and should be mapped accordingly.

Table 4: Visit Windows (Days)

Visit Name	Visit Number	Target Anchor	Relative Target Day	Visit Window
Baseline	1	Last visit from Study INS-212	1	-2 to 1
Month 1	2		30	23 to 37
Month 2	3		60	53 to 67
Month 3	4		90	83 to 97
Month 4	5		120	113 to 127
Month 5	6		150	143 to 157

Visit Name	Visit Number	Target Anchor	Relative Target Day	Visit Window
Month 6	7		180	173 to 187
Month 7	8		210	203 to 217
Month 8	9		240	233 to 247
Month 9	10		270	263 to 277
Month 10	11		300	293 to 307
Month 11	12		330	323 to 337
Month 12 (EOT)	13		365	353 to 367
Month 13 (EOS)	14		420	413 to 427

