### 3.6.2 Study Duration

Subjects will remain in the study for up to 13 months, up to 12 months in the open-label treatment phase plus 1 month in the off-LAI treatment phase. Each subject will receive treatment with LAI in the study for up to 12 months. Subjects will enroll directly from the INS-212 study at their EOT visit when all sputum results from Day 1 through Month 6 are known.

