## 6.4 END OF STUDY (UP TO MONTH 13, VISIT 14) DURING THE OFF-LAI TREATMENT PHASE

All the following should have performed or obtained  $\pm 3$  days of the scheduled visit:

- administer SGRQ (Part I and II) (see [Section 7.3.1](#))
- administer EQ-5D-3L (see [Section 7.3.2](#))
- administer physical examination, including vital signs, pulse oximetry and weight (see [Section 7.1.4](#) and [Section 7.1.3](#))
- solicit concomitant medications (see [Section 7.1.5](#))
- assess AEs (see [Section 7.1.1](#))

The EOS visit for all subjects, including those who prematurely discontinued the study, is scheduled to occur 1 month after the EOT visit.

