4. STUDY DESIGN

4.1. Summary of Study Design

Eligible subjects will have successfully completed their Month 6 visit in the INS-212 study. At or after all the INS-212 Month 6 visit assessments have been completed, the investigator will remind the subject of the potential opportunity to enroll in INS-312 at their scheduled Month 8 visit, to allow sufficient time for the subject to make an informed decision. At the scheduled Month 8 visit, eligible subjects will be confirmed to have not achieved the INS-212 protocol definition of culture conversion (3 consecutive negative sputum cultures) or to have experienced a relapse or recurrence (agar positive or more than 2 consecutive broth positive results after culture conversion has occurred), as determined by the subjects' Day 1 through Month 6 sputum assessments in INS-212. The scheduled Month 8 visit will become the EOT visit. Subjects will be asked to provide written informed consent and will enroll directly from the INS-212 study at their EOT visit when all sputum results from Day 1 through Month 6 are known, and after having met all eligibility criteria.

All enrolled subjects will receive ALIS administered QD added to a multi-drug regimen for 12 months. All subjects will return 1 month after EOT for an off-ALIS treatment follow-up visit at the end of study (EOS) visit.

The study schematic is in [Appendix X](#). The study time and events schedule is in [Appendix Y](#).

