6. GENERAL CONSIDERATIONS FOR DATA ANALYSES AND HANDLING

6.1. Data Presentation Conventions

Continuous variables will be summarized with means, standard deviations, medians, minimums, and maximums, and, if appropriate, by clinically relevant discretization's. Categorical variables will be summarized by counts and by percentage of subjects in corresponding categories. All data that meaningfully contribute to the objectives of the study will be included. Footnotes will specify the basis for the percentages. For counts of subjects, however, the denominator will generally be the number of subjects in the Safety population and treatment arm (based on treatment assignment in INS-212). All summary tables will be presented by treatment arm. A total summary column may be included in some summary tables wherever relevant.

Summaries of continuous variables that have some values recorded using approximate values (e.g., < or >) will use the numeric part of the value in calculations. Listings will present the data in its original format.

For summaries where rounding is required, rounding will be done to the nearest roundoff unit. For example, if the round-off unit is the ones place (i.e., integers), values $\geq XX.5$ will be rounded up to $XX+1$ while values $< XX.5$ will be rounded down to XX .

Individual subject data obtained from the electronic case report forms (eCRFs), and any derived data will be presented by treatment, site, and subject in data listings.

An unscheduled visit can be used in the determination of baseline values, if it provides the last non-missing value prior to the first dose of the study drug. Post-baseline unscheduled visit data will be presented in the listings only (i.e., unscheduled visit data will not be summarized in tables). If subject has more than one data at a specific visit for any reason, average of the data at that visit will be considered in summary tables.

The analyses described in this plan are considered a priori, in that they have been defined prior to database lock. Any other analyses performed will be considered post-hoc. Posthoc analyses will be labeled as such on the output and identified in the CSR.

All analyses and tabulations will be performed using SAS[®] version 9.4 or higher. Tables, listings, and figures will be created in rich text format.

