6.4.3. Study Day

Study day, the number of days from enrollment, is derived using the following formula:

$$\text{STUDYDAY} = (\text{assessment} - \text{enrollment date}) + (\text{assessment} \geq \text{enrollment date});$$

there is no study day 0.

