6.4.5. Duration

Duration is the time between two dates and may be expressed in days, months, or years. The formulae for deriving duration are:

- Duration (days) = end – start dates + 1
- Duration (months) = (duration [days])/30.4
- Duration (years) = (duration [days])/365.25

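### Table 4 of the final SAP misplaces the EOS window and mis-centres the EOT window, and 6.4.9 lets early stoppers' off-drug EOS values enter on-treatment months

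*SAP*

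**What the plan says.** Final SAP 6.4.9 takes visits at their nominal label, with EOT and EOS as the exceptions. When a subject stops early, the EOT visit replaces the planned visit, so it is also mapped to the coincident month. The worked example is a stop at Month 4, where the visit serves both the Month 4 and the EOT summaries. The section then adds "Similarly, for the EOS visit". Mapping is to be done where appropriate, a condition that is not defined. If the timing does not "coincide with a scheduled visit, it will not be mapped". If a subject has no EOT visit, the EOS visit also serves as EOT.

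Table 4 gives Month 12 (EOT) as Day 365, window 353 to 367, and Month 13 (EOS) as Day 420, window 413 to 427. Months 1 to 11 are each 30 days × the month number, ± 7.

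On timing, Protocol 6.4 says that EOS, for early stoppers too, "is scheduled to occur 1 month after the EOT visit". Final SAP 4.1 agrees: "All subjects will return 1 month after EOT for an off-ALIS treatment follow-up visit at the end of study (EOS) visit". Protocol 3.6.2 adds: "Subjects will remain in the study for up to 13 months". The schedules of events in both documents allow ± 3 days at EOT and at EOS.

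Final SAP 6.1 says that if a subject has more than one value at a visit, the "average of the data at that visit will be considered in summary tables".

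**The concern.** EOT and EOS are the two visits for which the section relies on windows rather than labels, and both rows look wrong. The targets are 55 days apart (420 − 365) where the documents call for one month. The EOT window is not symmetric about its own target, unlike the rows for Months 1 to 11.

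The mapping rule raises a different problem. EOS is by design an off-drug visit. If it is mapped to a calendar month in the same way as EOT, off-drug values are summarised as if they were on-treatment. Vital signs by visit belong to the primary safety endpoint, and SGRQ and EQ-5D-3L at Month 6 and Month 12/EOT are exploratory endpoints.

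**Working it through.** **Inputs.** Table 4 windows (final SAP 6.4.9); EOS one month after EOT (Protocol 6.4, final SAP 4.1); ± 3 days at each visit (schedules of events); "Study day, the number of days from enrollment", with enrolment as Day 1 (final SAP 6.4.3). Month length is not uniform: final SAP 6.4.4 divides study days by 30, while 6.4.5 has "Duration (months) = (duration [days])/30.4".

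**1. Can Day 420 be Month 13?** 13 × 30 = 390; 365 + 30 = 395; 13 × 30.4 = 395.2; 13 × 365.25/12 = 395.7. None gives 420. 14 × 30 = 420 does, and 14 is the visit number. That is a likely origin, though the SAP does not say so.

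**2. Where do on-schedule EOT and EOS visits fall?** Permitted EOT days are target ± 3. EOS day = EOT day + 28, 30 or 31, ± 3, which gives 7 × 3 × 7 = 147 combinations per target.

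| EOT target | Permitted EOT days | Outside 353–367 | EOS days | EOS in 413–427 |
|---|---|---|---|---|
| 360 (12 × 30) | 357–363 | none | 382–397 | 0 of 147 |
| 365 (Table 4) | 362–368 | 368 (1 of 7) | 387–402 | 0 of 147 |
| 366 (calendar year) | 363–369 | 368, 369 (2 of 7) | 388–403 | 0 of 147 |
| 367 (leap year) | 364–370 | 368–370 (3 of 7) | 389–404 | 0 of 147 |

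True calendar months over 1,461 start dates give 1,461 × 49 = 71,589 EOS combinations. None is in the window. The latest is Day 404, which is 413 − 404 = 9 days short. These days also lie in no other window, because Table 4 has none between Day 368 and Day 412.

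**3. EOT window.** Its centre is (353 + 367)/2 = 360, whereas 365 ± 7 would be 358 to 372. With calendar months, 3,287 of 10,227 permitted EOT days (32%, every day weighted equally) fall outside 353 to 367.

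**4. Early stoppers.** Let EOT be at the Month k visit (30k ± 3) and EOS 30 ± 3 days later. EOS is then on Day 30(k + 1) ± 6, inside the next month's ± 7 window in 49 of 49 combinations for every k from 1 to 11.
- Stop at Month 5: EOS on Days 174 to 186; Month 6 window 173 to 187.
- Stop at Month 11: EOS on Days 354 to 366; Month 12 (EOT) window 353 to 367.

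This uses Table 4's own 30-day targets. With a 31-day gap, all 49 still fall inside. With 28 days, one of 49 falls a day early.

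If a subject stops between visits, the result differs. Monthly windows cover 15 of every 30 days, so about half of the EOS dates would match no window.

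**5. Which summaries are exposed?** The schedule has SGRQ, EQ-5D-3L, vital signs, pulse oximetry and weight at EOS. It has no sputum, 6MWT, audiology or laboratory tests there. SGRQ and EQ-5D-3L have on-treatment rows only at Month 6 and Month 12/EOT, so only stops at Month 5 or 11 reach them (2 of 11 monthly stops). Vital signs have a row every month.

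**6. Check of the repair.** On-schedule EOS is 28 − 3 = 25 to 31 + 3 = 34 days after EOT, inside EOT + 30 ± 7 (23 to 37 days). A window of 353 to 372 holds every permitted EOT day in the table (357 to 370). Re-centring to 358 to 372 would lose Day 357 under 30-day months.

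**The case against.** The best defence is that mapping adds a visit to a second summary and does not remove it from its own. In the Month 4 example the visit counts in both, and final SAP 8.7.1 and 8.7.2 list EOS as a visit for SGRQ and EQ-5D-3L. A completer's EOS visit, or an EOT visit on Day 368, would then still be reported under its label. This stands. A reader might infer from the windows that completers' EOS data, or some on-time EOT data, are lost. The documents do not support that.

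Next, the EOT exclusion depends on how months are counted. With 30-day months, as in final SAP 6.4.4 and the other rows of Table 4, nothing is excluded. That also stands, but the target of 365 is then the error, so the row needs correcting either way.

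Third, EOS mapping is limited to where it is appropriate. The qualifier could be used to keep off-drug visits out, but it is undefined and nothing in the section excludes them. The fair description is that the rule permits the misplacement, not that it requires it in every case. Likewise, no text names averaging of EOT with a mapped EOS value. It follows from applying the general rule in 6.1 to two values in one row.

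Finally, the analyses are descriptive, with no hypotheses, and summarising post-discontinuation values by scheduled month can be defended if they are labelled as such. The section provides no such label.

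**Conclusion.** Both rows of Table 4 need correcting. The EOS error holds under every month convention tried: no on-schedule visit falls within 413 to 427, and the nearest is 9 days short. The EOT error is an inconsistency between target and window. It costs no permitted days with 30-day months, one of seven around Day 365, and two or three of seven with calendar months. Because visits may keep their labels, the harm may be confined to the windowed rows.

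The early-stopper rule has the more direct effect on content. When EOT was at a scheduled visit, off-drug EOS values can enter the next on-treatment month. Vital signs and weight are exposed generally. The exploratory SGRQ and EQ-5D-3L rows are exposed only for stops near Month 5 (Month 6 row) or Month 11 (Month 12/EOT row, where 6.1 would average them with the EOT value). The number of subjects involved depends on when they stop, which the documents do not give.

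It would be wrong to infer that the secondary efficacy results are compromised: neither culture conversion nor 6MWT is measured at EOS, so EOS mapping cannot affect them. Audiology and laboratory data are likewise unaffected. This should be corrected, but it does not threaten the study's main conclusions.

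**What to change.** In final SAP 6.4.9 and Table 4, before database lock:

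- Define the EOS window from each subject's own EOT date: EOT + 30 ± 7 days.
- State the month convention, and make the EOT target and window agree and cover both conventions, for example 353 to 372.
- State that EOS values taken off LAI are summarised only as EOS, are not mapped to Months 1 to 12, and are never averaged with an EOT value. This replaces the undefined condition on when mapping is appropriate.
- Where EOS stands in for a missing EOT visit, keep that rule but flag the value as off-LAI in the EOT summary.

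The cost is an edit to one table and a few sentences, with the matching programming. The downside is slightly fewer subjects in some by-visit rows.
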